6 INVESTIGATIONAL PLAN

6.1 Description of Overall Study Design and Plan

This is an open-label, sequential-dose escalation/de-escalation trial testing 3 dose levels of MT1002 in patients undergoing PCI due to ACS with NSTEMI. Three doses of MT1002 will be sequentially tested in cohorts of 6 patients each to achieve target ACT.

Pre-specified dose escalation/de-escalation/stopping/continuation rules for the patient cohorts are shown in Table 1 below.

Table 1 Rules for Dose Escalation/De-Escalation/Stopping/Continuation

Continue to next higher dose group if:	Stop study drug infusion temporarily in an individual patient if:	Stop dose group and de-escalate according to protocol if:	Continue the same dose in the next patient cohort (to get more data for initial dose) if:	Stop the study if:
$\leq 2/6$ pat peak ACT > 300	Any ACT > 350 or < 180	$\geq 3/6$ pat peak ACT > 300	$\leq 3/6$ pat peak ACT > 300	> 3/6 pat peak ACT > 350
≥ 3 pts. peak ACT < 200 (Cohort 2)				AND
$\leq 1/6$ pat with BARC 3 to 5	BARC 3 to 5	$\geq 2/6$ pat with BARC 3 to 5	$\leq 1/6$ pat with BARC 3 to 5	> 2/6 pat with BARC 3 to 5
				OR
No SAE due to study drug	Any AE/SAE due to study drug that requires switching patient to standard of care	$\geq 2/6$ SAEs due to study drug	No SAE due to study drug	$\geq 2/6$ SAEs due to study drug

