11.6 Adverse Events

11.6.1 Adverse Events

An AE is any symptom, physical sign, syndrome, or disease that either emerges during the study or, if present at Screening, worsens during the study, regardless of the suspected cause of the event. All medical and psychiatric conditions (except those related to the indication under study)

present at Screening will be documented in the medical history eCRF. Changes in these conditions and new symptoms, physical signs, syndromes, or diseases should be noted on the AE eCRF during the rest of the study. Clinically significant laboratory abnormalities should also be recorded as AEs.

Anticipated AEs

Anticipated AEs for this study population based on the results from the completed Phase 1 healthy volunteer study include bleeding (see also Section 11.6.3), allergic reactions, and headache.

Drug-related AEs which occurred in the completed Phase 1 study included headache, dizziness, discolored feces, mouth hemorrhage, injection site bruising and injection site nodule, and injection site hemorrhage.

Reporting of AEs

Patients will be instructed to report AEs at each study visit. All AEs are to be followed up until resolution or a stable clinical endpoint is reached.

Each AE is to be documented on the eCRF with reference to date of onset, duration, frequency, severity, relationship to study drug, action taken with study drug, treatment of event, and outcome. Furthermore, each AE is to be classified as being serious or nonserious. Changes in AEs and resolution dates are to be documented on the eCRF.

For the purposes of this study, the period of observation for collection of AEs extends from the time the patient gives informed consent until the end of study visit. Follow-up of the AE, even after the date of study drug completion, is required if the AE persists until the event resolves or stabilizes at a level acceptable to the Investigator.

When changes in the intensity of an AE occur more frequently than once a day, the maximum intensity for the event should be noted. If the intensity category changes over a number of days, then those changes should be recorded separately (with distinct onset dates).

Specific guidelines for classifying AEs by intensity and relationship to study drug are given in Table 7 and Table 8.

Table 7 Classification of Adverse Events by Intensity

Severity	Description

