11.6.3 Bleeding Events

Bleeding events are classified as major or minor based on BARC classification. Minor bleeding events are those that meet the criteria for BARC Type 2, and major bleeding events are those meeting the criteria for BARC Types 3 to 5.

BARC definitions are provided in Table 9.

Table 9 Bleeding Academic Research Consortium Definitions

Type	Definition
0	No bleeding
1	Bleeding that is not actionable and does not cause the patient to seek treatment
2	Any clinically overt sign of hemorrhage that “is actionable” and requires diagnostic studies, hospitalization, or treatment by a health care professional
3	
 Overt bleeding plus hemoglobin drop of 3 to < 5 g/dL (provided hemoglobin drop is related to bleed); transfusion with overt bleeding Overt bleeding plus hemoglobin drop < 5 g/dL (provided hemoglobin drop is related to bleed); cardiac tamponade; bleeding requiring surgical intervention for control; bleeding requiring intravenous vasoactive agents Intracranial hemorrhage confirmed by autopsy, imaging, or lumbar puncture; intraocular bleed compromising vision
4	Coronary artery bypass grafting-related bleeding within 48 hours
5	
 Probable fatal bleeding Definite fatal bleeding (overt or autopsy or imaging confirmation)

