11.6.5 Serious Adverse Events

An SAE is any untoward medical occurrence, in the view of either the Investigator or Sponsor, that:

- results in death,
- is life-threatening,
- results in inpatient hospitalization or prolongation of existing hospitalization,
- results in persistent or significant disability/incapacity, and/or
- is a congenital anomaly/birth defect

Other important medical events that may not be immediately life-threatening or result in death or hospitalization, based upon appropriate medical judgment, are considered SAEs if they are thought to jeopardize the patient and/or require medical or surgical intervention to prevent one of the outcomes defining an SAE. SAEs are critically important for the identification of significant safety problems; therefore, it is important to take into account both the Investigator's and the Sponsor's assessment. If either the Sponsor or the Investigator believes that an event is serious, the event must be considered serious and evaluated by the Sponsor for expedited reporting.

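### Table 1's SAE row sends two drug-related SAEs to both de-escalation and study stop and leaves one without an action, and serious drug-related major bleeds fall under that row

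*Combined protocol and SAP*

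**What the plan says.** Section 6.1 sets the frame: "Three doses of MT1002 will be sequentially tested in cohorts of 6 patients each to achieve target ACT". Table 1 has four cohort-level columns (escalate, continue the same dose, de-escalate, stop the study) and one column for interrupting the infusion in an individual patient. Two rows matter here.

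- **BARC row.** Escalating or continuing the same dose allows at most 1 of 6 patients with a BARC 3 to 5 bleed. De-escalation applies from 2 of 6. The study stops at more than 2 of 6, but only together with more than 3 of 6 patients with peak ACT above 350. The row carries no condition on cause or seriousness.
- **SAE row.** Escalating or continuing the same dose requires "No SAE due to study drug". The de-escalation cell and the study-stop cell carry identical text, "\geq 2/6$ SAEs due to study drug" (that is, two or more). In the stop column it is joined by OR, so no ACT condition applies to it.

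Section 11.6.3 states that "major bleeding events are those meeting the criteria for BARC Types 3 to 5". Section 11.6.5 counts as serious, besides death, life-threatening events and prolonged hospitalization, events judged to "require medical or surgical intervention to prevent one of the outcomes defining an SAE". Section 11.6.1 says: "Anticipated AEs for this study population based on the results from the completed Phase 1 healthy volunteer study include bleeding". The synopsis copy of Table 1 has the same limits in both rows.

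**The concern.** A prespecified decision table should lead from each observed count to one action. The SAE row does not: the same count appears under two actions of very different weight, and a count of one leads nowhere at cohort level. This holds for any drug-related SAE, for instance two hypersensitivity reactions.

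It matters most for bleeding, because major bleeding is a co-primary endpoint and the main expected hazard of the drug. No text assigns a bleed that fits both rows to one of them. Such a bleed is subject to the SAE row, which is stricter for going on and reaches a study stop sooner. It also bypasses the joint ACT and bleeding condition. The version 6.0 entry in the change history explains that condition by saying that a high ACT and major bleeding are both needed to justify a stop.

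**Working it through.** The documents give no operating characteristics for Table 1, so there is no figure to reproduce. I applied the columns to each count and then attached illustrative probabilities.

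**Step 1: actions by count.** Take k patients in a cohort of 6, each with one major bleed that is also a drug-related SAE, with the ACT and laboratory criteria otherwise satisfied. I read the criteria within each of the two going-on columns as all required; the table does not say so.

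| k | BARC row | SAE row |
|---|---|---|
| 0 | going on allowed | going on allowed |
| 1 | going on allowed | going on barred; no other cohort-level cell met |
| 2 | de-escalate | de-escalate and stop the study |
| 3 or more | de-escalate; stop only if more than 3 of 6 also have peak ACT above 350 | de-escalate and stop the study, whatever the ACT |

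The SAE column of this table is the same for drug-related SAEs that are not bleeds.

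**Step 2: inputs for the illustration.** n = 6 (Table 1). The per-patient risk of a major bleed, p, is not in the documents; I assume 10%, with 5% and 20% as a range. The share q of major bleeds that are both serious and attributed to the drug is also not given; I use 0, 0.5 and 1. Patients are taken as independent, each with at most one event, and no other SAEs occur.

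**Step 3: chance that both rows allow going on.** This needs either no major bleed, or exactly one that is not a drug-related SAE:

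(1−p)^6 + 6p(1−q)(1−p)^5

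At p = 0.10, 0.9^6 = 0.5314 and 6 × 0.1 × 0.9^5 = 0.3543.

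- q = 0: 0.5314 + 0.3543 = 0.8857
- q = 0.5: 0.5314 + 0.5 × 0.3543 = 0.7086
- q = 1: 0.5314

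The 0.3543 is also the chance of exactly one major bleed, the count at which the two rows differ on going on when q = 1.

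**Step 4: chance of reaching a stop count.** The SAE row needs at least 2 events from a binomial with n = 6 and probability pq. At p = 0.10 and q = 1 this is 1 − 0.5314 − 0.3543 = 0.1143. The BARC part needs at least 3 bleeds: 0.1143 − 15 × 0.1² × 0.9^4 = 0.1143 − 0.0984 = 0.0159. That is an upper bound for the bleeding arm, because the ACT condition must also hold.

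**Step 5: range.**

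| p | Going on, q = 0 / 0.5 / 1 | Stop count by SAE row, q = 0.5 / 1 | Stop count by BARC part, upper bound |
|---|---|---|---|
| 5% | 96.7% / 85.1% / 73.5% | 0.9% / 3.3% | 0.2% |
| 10% | 88.6% / 70.9% / 53.1% | 3.3% / 11.4% | 1.6% |
| 20% | 65.5% / 45.9% / 26.2% | 11.4% / 34.5% | 9.9% |

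**The case against.** A reader might infer that the BARC limits never operate because the SAE row always overrides them. The documents do not support that. The BARC row counts bleeds of any cause, so it still governs those that are not serious or not attributed to the drug. A hemoglobin fall of 3 to under 5 g/dL without intervention is not automatically an SAE under Section 11.6.5. Attribution is not automatic either: listing bleeding as anticipated is not a causality rule, patients also take aspirin and a P2Y12 inhibitor and undergo arterial-access PCI, and Section 8.5.1 asks for SAE causality to be assessed against those background drugs too. With q = 0 the BARC limit works as written.

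A reader might also infer that the two rows contradict each other over a single bleed. Read jointly, the going-on columns are coherent: at most one major bleed, and no drug-related SAE. Nor does the clash at two events come from the overlap. Both rows de-escalate at 2 of 6; the clash arises because the SAE row repeats its limit in the stop column. Assigning bleeds to one row would leave that fault in place for every other SAE.

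Finally, the Study Management Group decides using the criteria together with other data, and it includes an independent cardiologist. So the probabilities above describe the written limits, not the group's final decisions. But discretion does not repair a table that attaches two actions to one count and none to another.

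That the SAE row might count events, so that one patient with two SAE terms would reach the limit, is a weaker point. The denominator of six suggests patients, but the cell says SAEs where the other rows say patients, so a clarification is warranted.

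**Conclusion.** The decision rule is faulty in the SAE row for any kind of drug-related SAE: two events trigger both de-escalation and study stop, and one event bars going on without meeting another cohort-level column. Because bleeds are not kept out of the row, a major bleed that is also a drug-related SAE meets the BARC limit for going on when it occurs once but fails the SAE limit. Two or more such bleeds stop the study without the joint ACT and bleeding condition.

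These conclusions follow from the printed cells, given the joint reading of the going-on columns. The size depends on assumed values. At a 10% risk, the SAE row lowers the chance of going on by 17.7 percentage points if half the major bleeds are drug-related SAEs (88.6 − 70.9) and by 35.5 points if all are (88.6 − 53.1). Neither the risk nor the share can be taken from the documents. The six patients of cohort 1, reported to have had no SAE or major bleed, are too few to fix them.

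**What to change.** Reconcile the de-escalation and study-stop cells of the SAE row. State how a BARC 3 to 5 bleed that is also a drug-related SAE is counted across the BARC and SAE rows. Every count, including a single event, should lead to one action. Clarify whether the SAE limit counts patients or events. Use the same text in Table 1, the synopsis table and the Study Management Group charter. Which limit applies is for the sponsor and the Study Management Group to settle; none is proposed here.

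The cost is a clause and a clarification of the counting unit in those three places. No further data or patients are needed.

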In $\leq 1/6$ pat lab values preventing dose escalation such as LFT up by $\geq 2 \times$ from baseline; platelet count < 50,000; QTcF interval > 500 ms or > 60 ms change from baseline, based on ECGs; or study drug related vital sign changes that require stabilization of hemodynamics with positive inotropes	Lab values preventing dose continuation such as LFT up by $\geq 2 \times$ from baseline; platelet count < 50,000; QTcF interval > 500 ms or > 60 ms change from baseline, based on ECGs; or study drug related vital sign changes that require stabilization of hemodynamics with positive inotropes	In $\geq 2/6$ pat lab value preventing dose escalation such as LFT up by $\geq 2 \times$ from baseline; platelet count < 50,000; QTcF interval > 500 ms or > 60 ms change from baseline, based on ECGs; or study drug related vital sign changes that require stabilization of hemodynamics with positive inotropes	In $\leq 1/6$ pat lab values preventing dose escalation such as LFT up by $\geq 2 \times$ from baseline; platelet count < 50,000; QTcF interval > 500 ms or > 60 ms change from baseline, based on ECGs; or study drug related vital sign changes that require stabilization of hemodynamics with positive inotropes	In $\geq 3/6$ pat lab values preventing dose escalation such as LFT up by $\geq 2 \times$ from baseline; platelet count < 50,000; QTcF interval > 500 ms or > 60 ms change from baseline, based on ECGs; or study drug related vital sign changes that require stabilization of hemodynamics with positive inotropes

Abbreviations: AE, adverse event; ACT, activated clotting time; BARC, Bleeding Academic Research Consortium; ECG, electrocardiogram; LFT, liver function test; pat, patient; QTcF, QT interval corrected by Fridericia's formula; SAE, serious AE.

The decision on dose escalation/de-escalation/stopping or continuation for the patient cohort will be taken by the Study Management Group based on data review of each dose group considering safety, efficacy, drug concentration, and in conjunction with the prespecified criteria.

End of Cohort 1 SMG meeting held on March 23, 2023 recommended to proceed to cohort 3 if patients in cohort 2 shows insufficient anticoagulation effect. Insufficient anticoagulation effect is defined when 3 patients or more treated within cohort 2 dosing regimen experienced at least one ACT<200 seconds and confirmed by Ad Hoc SMG meeting.

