9 STUDY PROCEDURES

Table 4 outlines the timing of procedures and assessments to be performed throughout the study. Section 11.5 specifies laboratory assessment samples to be obtained. See Sections 100 and 111 for additional details regarding efficacy/pharmacodynamic assessments and safety assessments, respectively.

Table 4 Schedule of Assessments

Assessment	Screening	Day of Procedure, Day 1			Follow-up		
Study Day	On admission	Pre PCI (Baseline)	During PCI ^a (≤ 72 hours from admission depending on the risk criteria)	Post PCI	Day 2 ^b	Day 14±1	End of Study Day 30±2
Informed consent	X						
Inclusion/exclusion criteria	X	X					
Significant medical and surgical history	X						
Demographics	X						
Cardiac and noncardiac medication on	X						
Physical examination ^c	X			X	X	X	X
Weight, height, body mass index	X						
Vital signs		X ^l	X	X	X	X	X
12-lead electrocardiogram		X ^l		X	X	X	X
CK-MB, cardiac troponin I (or troponin T) ^d		X ^l X	X	X	X	X	X
ACT, aPTT, PT, TT, FIB, INR		X ^l	X ^k	X	X	X	X
PA (by PFA100 or PFA200) ^e		X ^l	X	X	X	X	X
Hematocrit, hemoglobin, platelet count, RBC and WBC counts		X ^l	X	X	X	X	X
Serum chemistry including lipid panel and HbA1c ^f	X				X	X	X
Serum or urine pregnancy test (women of childbearing potential only)	X						X
Percutaneous coronary intervention			X				
Aspirin ^g	X	(X)			◀-----▶		
Clopidogrel (or Ticagrelor or Prasugrel) ^h	X	(X)			◀-----▶		
Enrollment to MT1002		X					
Administration of MT1002 ⁱ		X	X	X			
TIMI flow grade		X	X				
Pharmacokinetic blood sampling ^j		X	X	X	X		
Concomitant medication review	X	X	X	X	X	X	X
Bleeding adverse events (BARC)		X	X	X	X	X	X
Other adverse events	X						

Assessment	Screening	Day of Procedure, Day 1			Follow-up		
Study Day	On admission	Pre PCI (Baseline)	During PCI ^a (≤ 72 hours from admission depending on the risk criteria)	Post PCI	Day 2 ^b	Day 14±1	End of Study Day 30±2
Discharge					X		
Study close out							X

Abbreviations: ACT, activated clotting time; aPTT, activated partial thromboplastin time; BARC, Bleeding

Academic Research Consortium; CK, creatine kinase; HbA1c, glycosylated hemoglobin; min, minutes; PA, platelet aggregation; PCI, percutaneous coronary intervention; PT, prothrombin time; RBC, red blood cell; sec, seconds; TIMI, thrombolysis in myocardial infarction; WBC, white blood cell.

- ^a PCI should start after MT1002 initiation as soon as ACT is confirmed to be ≥ 200 sec or within 30 min after MT1002 start, whichever occurs first.

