- ^b Day 2 lasts until 24 hours ± 1 hour after the MT1002 intravenous injection start on Day 1 and until study-related procedures are complete. Patients will be discharged from the hospital when they are stable according to local standard of care.
- ^c Physical examination is to be performed on Admission Day 1 and includes general appearance, head, eyes, ears, nose, and throat; and cardiovascular, respiratory, gastrointestinal, dermatological, neurological, musculoskeletal, lymphatic, and other systems at the discretion of the Investigator. Brief physical examination should be performed on all other visits from Post-PCI Day 1 onwards and includes general appearance, cardiovascular, respiratory, gastrointestinal, and other at the discretion of the Investigator.
- ^d CK-MB, cardiac troponin I (troponin T can be measured if the local site does not have the troponin I test) to be collected at Screening; immediately before PCI (Day 1 predose); and 0.5 (± 5 mins), 4 (-5 to 10 mins, 5-10 min before the infusion completion), 6 (± 15 mins), 8 (± 15 mins), and 24 (± 15 mins) hours post dose initiation.
- ^e The PA (by PFA100 or PFA200) test should be conducted within 15 min of sample collection. Platelet aggregation sampling to be done at Screening; at 5 (± 1) min after MT1002 intravenous injection; and 0.5 (± 5 mins), 4 (-5 to 10 mins, 5-10 min before the infusion completion), 6 (± 15 mins), 8 (± 15 mins), and 24 (± 15 mins) hours post dose initiation.
- ^f Lipid panel only assessed at Screening and Day 30; HbA1c assessed at Screening only. For the other chemistry parameters, see Section 11.5.
- ^g Aspirin approximately 325 mg (not exceeding 400mg) loading dose on admission, followed by 75-100 mg/day (according to local countries clinical practice guidance). No loading dose if patient is already on chronic treatment with aspirin.
- ^h Clopidogrel 600 mg loading dose on admission, followed by 75 mg/day. If the local clinical guidance recommends use of Ticagrelor or Prasugrel, the recommended doses will be: Ticagrelor 180 mg loading dose on admission, followed by a maintenance dose of 90 mg twice daily. Or Prasugrel 60 mg loading dose on admission, followed by a maintenance dose of 5-10 mg daily. No loading dose if patient is already on chronic treatment with clopidogrel or Ticagrelor or Prasugrel.

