- Administer study drug via IV access before the PCI and record time of dosing in the eCRF. Study drug should be administered in catheterization lab as close to randomization and the start of the PCI procedure as possible.
- Conduct a visual bleeding inspection and assess bleeding AEs according to the BARC criteria; record any patient-reported bleeding.
- Record any other AEs that have occurred.

9.2.3 During Percutaneous Coronary Intervention, Day 1

Either radial access/distal radial access PCI or femoral access PCI will be used in this study. It is up to the discretion of the Principal Investigator what type of stent(s) will be used.

- Conduct the PCI procedure per local standard of care.
- Record TIMI flow grade post PCI.
- Patients who fail to achieve ACT target of 200 to 300 sec with MT1002 (within 30 minutes after MT1002 infusion initiation) before PCI will be switched to standard of care (UFH or bivalirudin, see Section 8.5.1).
- Patients who achieve ACT target of 200 to 300 sec with MT1002 (within 30 minutes after MT1002 infusion initiation) before PCI should continue the study drug infusion for 4 ± 0.5 hours after infusion start.
- Monitor patients for potential AEs, including allergic reactions during the MT1002 administration.
- Record vital signs (body temperature, respiration rate, heart rate, and systolic and diastolic blood pressure).
- Record any procedural complications, as well as any other AEs
 - Glycoprotein IIb/IIIa inhibitors may be used for procedural or angiographic complications only (dosing per local standard of care, see Section 8.5.1)
 - In those patients who experience significant intracoronary thrombosis during the procedure, or experience acute thrombosis after the procedure, heparin bail out may be administered (see Section 8.5.1).
- Perform a PA (by PFA100 or PFA200) according to the time points in the Schedule of Assessments (Table 4) and Table 5.

- Obtain central cardiac biomarkers (troponin I [troponin T can be measured if the local site does not have the troponin I test], and CK-MB) according to the time points in the Schedule of Assessments (Table 4) and Table 5.
- Obtain coagulogram (ACT, aPTT, PT, TT, FIB, INR according to the time points in the Schedule of Assessments [Table 4] and Table 5), hemoglobin, hematocrit, platelet count, RBC, and WBC counts.
- Obtain PK samples according to the time points in the Schedule of Assessments (Table 4) and Table 5.

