- Conduct a visual bleeding inspection and assess bleeding AEs according to the BARC criteria; record any patient-reported bleeding.
- Record all changes in concomitant medications.
- Obtain a copy of the PCI procedure report and record information about index-procedure (e.g., but not limited to vascular access, lesions treated, stents used, procedure result). Successful treatment with PCI is defined as achievement of < 30% residual diameter stenosis of all treated lesions assessed by visual inspection or quantitative coronary angiography, without an in-hospital major adverse cardiac event (death, MI or repeat coronary revascularization of the target lesion).

9.2.4 Post Percutaneous Coronary Intervention, Day 1

- Record end of PCI time in the eCRF. End of procedure is defined as the date/time when the last coronary catheter (all catheters other than arterial sheath or intra-aortic balloon positioning) is removed from the body.
- Continue MT1002 infusion for 4 hours after infusion start (including post-PCI).
- Remove the sheath approximately 3 hours after MT1002 infusion is complete. Record sheath removal time in the eCRF.
- Perform a brief physical examination.
- Record vital signs (body temperature, respiration rate, heart rate, and systolic and diastolic blood pressure).
- Perform a 12-lead ECG.
- Perform a PA (by PFA100 or PFA200) according to the time points in the Schedule of Assessments (Table 4) and Table 5.
- Collect blood samples for hematology, coagulogram, and cardiac biomarkers (refer to Section 11.5 for parameters included)
 - CK-MB, cardiac troponin I (troponin T can be measured if the local site does not have the troponin I test) according to the time points in the Schedule of Assessments (Table 4) and Table 5
 - ACT, aPTT, PT, TT, FIB, INR as per time points in the Schedule of Assessments (Table 4) and Table 5
 - Hematocrit, hemoglobin, platelet count, RBC and WBC counts according to the time points in the Schedule of Assessments (Table 4)

This document is confidential.

- Obtain PK samples according to the time points in the Schedule of Assessments (Table 4) and Table 5.
- Record all changes in concomitant medications.
- Conduct a visual bleeding inspection and assess bleeding AEs according to the BARC criteria; record any patient-reported bleeding
 - Immediately upon achievement of hemostasis, with time of complete hemostasis recorded on the eCRF;
 - Thereafter, per local standard of care
- Record any other AEs that have occurred.

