11.5 Laboratory Assessments

The hematology and clinical chemistry laboratory analyses will be performed at local laboratories. Reference ranges will be supplied by local laboratories and used by the Investigator to assess the laboratory data for clinical significance and pathological changes.

Laboratory assessment samples (Table 6) are to be obtained at designated visits as detailed in the Schedule of Assessments (Table 4).

Table 6 Laboratory Assessments

Hematology	Serum Chemistry
Hct Hb Platelet count RBC count WBC count with differential	ALT AST BUN or urea Creatinine Creatine kinase and subtypes Electrolytes (sodium, potassium) Glucose LDH Total bilirubin Direct bilirubin Total protein Lipid panel eGFR HbA1c
Coagulation	Others
PT Activated PTT ACT TT FIB INR PA (by PFA100 or PFA200)	CK-MB Cardiac troponin I or troponin T (troponin T can be measured if the local site does not have the troponin I test)
Pregnancy test: A pregnancy test (serum or urine) will be performed on all women of childbearing potential at Screening and at End of Study (Day 30±2).	

Abbreviations: ACT, activated clotting time; ALT, alanine aminotransferase; AST, aspartate aminotransferase; BUN, blood urea nitrogen; CK, creatine kinase; eGFR, estimated glomerular filtration rate; Hb, hemoglobin; HbA1c, glycosylated hemoglobin; Hct, hematocrit; LDH, lactate dehydrogenase; PT, prothrombin time; PTT, partial thromboplastin time; RBC, red blood cell; WBC, white blood cell.

Blood samples will be analyzed at a local laboratory facility. All laboratory reports must be reviewed, signed, and dated by the Investigator. A legible copy of all reports must be filed with both the patient's eCRF and medical record (source document) for that visit. Any laboratory test result considered by the Investigator to be clinically significant should be considered an AE (clinically significant AEs include those that require an intervention). Clinically significant abnormal values occurring during the study will be followed up until repeat test results return to normal, stabilize, or are no longer clinically significant.

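### Table 1 interrupts an infusion for liver-test or QTcF changes, but the schedule assures neither measurement while the drug is running, so QTcF counts can rest on off-drug ECGs

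*Combined protocol and SAP*

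**What the plan says.** Table 1 (Section 6.1, and the matching synopsis table) has a column of reasons to interrupt one patient's infusion. Its last row lists "Lab values preventing dose continuation such as LFT up by" at least 2 × baseline, a platelet count below 50,000, QTcF above 500 ms or changed by more than 60 ms, and vital-sign changes needing inotropes. The same laboratory and ECG items are counted per cohort in the escalation, de-escalation, same-dose and study-stop columns.

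Patients who reach the ACT target "should continue the study drug infusion for 4 ± 0.5 hours after infusion start" (Section 9.2.3), and Section 9.2.4 has the infusion run on after PCI. Footnote a of Table 4 says "PCI should start after MT1002 initiation as soon as ACT is confirmed to be" at least 200 sec, or within 30 minutes of drug start.

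The schedule in Table 4 and Sections 9.2.1 to 9.2.6 gives:

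- **Liver tests.** Table 6 places ALT, AST and bilirubin under serum chemistry. The Table 4 row "Serum chemistry including lipid panel and HbA1c" is marked at Screening, Day 2, Day 14 and Day 30. Sections 9.2.2 to 9.2.4 list no chemistry.
- **ECG.** Marked Pre PCI, Post PCI, Day 2, Day 14 and Day 30, and blank During PCI. For the post-PCI period, Section 9.2.4 says only "Perform a 12-lead ECG".
- **Platelet count.** Marked Pre, During and Post PCI, then at each later visit. Section 9.2.3 repeats the During-PCI draw.
- **Clock-timed tests.** Table 5 times only platelet aggregation, cardiac biomarkers, coagulation and PK, with one point 5 to 10 minutes before the infusion finishes.

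Section 14.4 tabulates QTcF above 450, 480 and 500 msec and changes above 30 and 60 msec. It does not say which ECG counts as on treatment.

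**The concern.** A criterion for interrupting a running infusion is useful only if the measurement can exist while the infusion runs. Here the two schedules do not meet. Liver chemistry is next due the following day, and the one Day 1 post-dose ECG may be taken at any time after PCI.

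The larger stake is the QTcF evidence. QTcF counts feed every cohort-level column of Table 1 and the Section 14.4 tables, in a study whose primary objective is a safe and well tolerated dose. If the Day 1 ECG is taken after the infusion has ended, a clean count may show only that the drug had cleared. Section 4.2.2 describes elimination in humans as fast, so Day 2 and later ECGs cannot fill the gap.

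**Working it through.** The plan states no figure on this point to reproduce. The check sets the schedule against the infusion window.

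**1. Gap from infusion end to the first scheduled post-dose liver test**

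Inputs: infusion length 4 ± 0.5 h (Section 9.2.3). For the visit limit, Table 4 footnote b says "Day 2 lasts until 24 hours ± 1 hour after the MT1002 intravenous injection start on Day 1".

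Gap = time of Day 2 draw − infusion length.

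- Nominal: 24 − 4 = 20 h
- Shortest at the limit: 23 − 4.5 = 18.5 h
- Longest at the limit: 25 − 3.5 = 21.5 h

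These figures place the draw at the 24 ± 1 h limit. A draw earlier on Day 2 would shorten the gap, but no chemistry is scheduled at any Day 1 step after dosing.

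**2. Scheduled measurements that must fall within the infusion**

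- Liver tests: 0.
- ECG: 0 assured. There is one untimed Post-PCI ECG, on or off drug.
- Platelet count: 1 (During PCI), plus one untimed Post-PCI count. PCI starts after the drug and the infusion outlasts it, so for a patient still on MT1002 the During-PCI count is an on-infusion sample.

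**3. Where the Post-PCI ECG can fall**

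PCI duration is not given. Assume PCI ends t = 0.5 to 3 h after infusion start. On-infusion time left = 4 − t, which runs from 4 − 0.5 = 3.5 h down to 4 − 3 = 1 h. The post-PCI section also covers sheath removal about 3 h after the infusion is complete and, through Table 5, samples at 6 and 8 h. An ECG on either side of infusion end therefore complies.

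**4. Illustration of what an off-drug ECG would see**

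The documents give no half-life. Assume single-exponential decline with a half-life h of 0.3 to 1 h, and an ECG taken d hours after infusion end. Fraction of the end-of-infusion concentration remaining = 0.5^(d/h):

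- d = 0.5 h: 0.5^(0.5/0.3) = 0.31 to 0.5^(0.5/1) = 0.71
- d = 1 h: 0.5^(1/0.3) = 0.10 to 0.5^(1/1) = 0.50
- d = 2 h: 0.5^(2/0.3) = 0.01 to 0.5^(2/1) = 0.25
- d = 3 h: 0.5^(3/0.3) = 0.001 to 0.5^(3/1) = 0.125

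An ECG taken while the infusion is still running loses nothing. Steps 1 to 3 do not depend on this illustration.

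**The case against.** The strongest case on the other side has five parts.

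- **Nothing puts the ECG off drug.** The post-PCI period includes the rest of the infusion, and many sites may record the ECG soon after PCI. This stands. The defect is an unfixed time, and off-drug QTcF is a possibility that the plan leaves open.
- **The liver item can be met by other means.** Section 9.2 allows unscheduled assessments at the investigator's discretion, chemistry is run locally, and the liver test is one example in an open list. This also stands. It limits the statement to scheduled data, but a discretionary test does not make a routine safeguard.
- **Cohort decisions have liver data.** The Study Management Group meets after each cohort and can use Day 2 chemistry. That is correct, so the liver point is confined to the individual-patient column.
- **The prior QT concern is low.** Section 4.2.1.4 reports a hERG IC50 above 100.67 μmol/L and no cardiovascular effect in dogs. This lowers the stakes. The sponsor nevertheless made QTcF a criterion in every column, so it should be measured when it is informative.
- **The SAP may define on-treatment QTcF.** Section 14 defers variable definitions to a later SAP whose text is not in the document reviewed. It may do so, but no analysis definition can supply an ECG that was not taken on drug.

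A reader might infer more than this. The platelet criterion is not unobservable in the same way, since a During-PCI count is scheduled on infusion and lacks only a clock time. Nor can one say that no liver test is drawn on Day 1, because Section 11.1 allows Screening to fall on that day. Only a post-dose draw is absent.

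**Conclusion.** The point holds for the liver and QTcF items. No scheduled post-dose liver test exists until Day 2, 18.5 to 21.5 h after infusion end at the visit limit, so scheduled data cannot trigger the liver item in the individual column. No on-infusion ECG is assured, so the QTcF item there may have nothing to act on, and the QTcF counts in Table 1's cohort columns and Section 14.4 can rest on off-drug ECGs.

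The liver gap rests on the schedule alone. How much signal an off-drug ECG would lose cannot be stated from the documents. The fractions above rest on an assumed half-life and assumed delays, and show only that an hour or two could matter for a rapidly eliminated drug. It does not follow that the QTcF data will be uninformative, or that no patient could ever meet the liver criterion. The change is worth making because it is almost free and secures on-drug QTcF data for the dose decisions.

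**What to change.** 1. **Time the existing ECG.** In Table 4, Table 5 and Section 9.2.4, attach the Post-PCI ECG to the PK and coagulation point 5 to 10 minutes before infusion completion, and record its clock time. Anchor it to completion rather than to the nominal 4 h, because a 3.5 h infusion ends before that clock time. In Section 14.4 and the SAP, define on-treatment QTcF change as the last pre-dose ECG to this ECG. For patients whose infusion ends early, use the recorded times to class the ECG as on or off drug. This serves the QTcF evaluation and the cohort reviews. So close to completion, it is not a means of stopping that same infusion.

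2. **Reconcile Table 1 with the schedule.** The liver and QTcF items in the individual-infusion column and the assessment times in Tables 4 and 5 must be brought into agreement. Which side changes is for the sponsor and its clinical advisers, and no threshold or clinical rule is proposed here.

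The cost is a timing footnote, one analysis definition and the small burden of doing one already scheduled ECG at a set time. The first change adds no visit, blood draw or ECG.
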